8.5.3.3 Safety Population

The safety population consists of all enrolled patients who have received at least one dose of lomitapide.

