8.3.1.1 Regional Study Site Enrolment Visit

At the LOWER enrolment visit, after the patient has provided written consent to participate in LOWER, the LOWER enrolling physician (or designee) will provide an overview of this vascular imaging study to each patient. The LOWER enrolling physician will notify the SCC of interested patients. The SCC will then notify the regional study

site. The regional study site will contact the patient to assess eligibility and obtain informed consent. For patients who are not located near the regional site, verbal informed consent will be obtained first by phone with written informed consent obtained at the baseline visit, prior to any procedures being performed. Enrolled patients will have a baseline MRI scan at the regional study site prior to initiating lomitapide therapy or within three months after initiating lomitapide therapy.

The following will be collected at the enrolment visit:

- Date of written informed consent
- Confirmation of eligibility criteria
- Laboratory tests (lipoprotein, inflammatory and cardiovascular biomarkers)
 - Lipoprotein biomarkers
 - Total cholesterol (TC)
 - High density lipoprotein (HDL-C)
 - Low density lipoprotein (LDL-C)
 - Triglycerides (TG)
 - Apolipoprotein B (apo B)
 - Apolipoprotein A-I (apo AI)
 - Lipoprotein (a) (Lp(a))
 - Apolipoprotein C-III (Apo C-III)
 - LDL sub-fractions using nuclear magnetic resonance (NMR) technology
 - Inflammatory and cardiovascular biomarkers
 - High sensitivity C reactive protein (hs-CRP)
 - Serum amyloid A (SAA)
 - Soluble Inter-cellular Adhesion Molecule-1 (sICAM-1)
 - Interleukin 6 (IL-6)
 - Lipoprotein Associated Phospholipase 2 (LpPLA2)
 - Soluble Vascular Cell Adhesion Protein 1 (sVCAM-1)
 - Soluble E-selectin (sE-selectin)

- Fasting glucose and insulin and calculate HOMA (Homeostasis Model Assessment)
- Baseline MRI

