8.3.1.2 Baseline MRI Scan

In order to be eligible for this study, a patient must have his/her baseline MRI scan within three months after initiating therapy with lomitapide. The baseline MRI should ideally be scheduled as soon as possible after enrolment and prior to initiation of lomitapide therapy.

Patients must have a baseline MRI scan that is deemed evaluable with an acceptable image quality of carotid arteries (both left and right carotid arteries) and aorta as determined by the central Imaging Core Laboratory in order to proceed to the follow up visits. All MRI scans must be immediately sent to the central Imaging Core Laboratory for qualitative image analysis. The central Imaging Core Laboratory will provide a rapid turnaround (within one week) of the image quality evaluation. The image quality evaluation will be sent to the regional study site as well as to the SCC so that, in the event that a repeat MRI is required, the site can contact the patient to return for additional scans.

Each regional study site will provide data to the central Imaging Core Laboratory following the guidelines set forth in the MRI Imaging Facility Charter ([Section 8.3.2](#)). The central Imaging Core Laboratory will notify the regional study site and the SCC that the MRI is acceptable, or if a repeat MRI is required. The SCC will request that the regional study site Investigator or his/her designee either complete the notification form if the testing was completed or contact the patient and schedule a repeat MRI. An MRI image deemed acceptable by the central Imaging Core Laboratory must be confirmed within three months of the patient starting lomitapide treatment. If delays result in the imaging being done outside of the three month window since starting lomitapide treatment, the patient will not be eligible to continue in the study.

The central Imaging Core Laboratory will transfer analysed results to SCC in a pre-specified format and time-frame as specified in the DMP.

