8.5.4.5 Safety

Safety specific to this sub-study will be evaluated for adverse events (AEs) and serious adverse events (SAEs) associated with the MRI procedures and clinical laboratory monitoring, using the safety population.

All other safety information, including MACE events, will be obtained from the data collected as part of each patient's participation in the global lomitapide registry, LOWER. A summary of study drug exposure, including the durations of the therapy and doses, and the proportions of patients with modifications in therapy, will be produced.

Adverse events for the sub-study safety population, collected as part of the LOWER study, will be summarized by the Medical Dictionary for Regulatory Activities (MeDRA) system organ class and preferred term. Separate tabulations will be produced for all treatment emergent AEs, treatment-related AEs (those considered by the LOWER enrolling physician as at least possibly drug related), SAEs, and discontinuations due to AEs. By-patient listings will be provided for deaths, SAEs, and events leading to discontinuation of treatment.

Descriptive statistics will be provided for clinical laboratory data, presented as both actual values and changes from baseline relative to each on-study evaluation and to the last evaluation on study, as well as shifts relative to normal ranges.

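### Procedure-related adverse events are summarised in a population that requires a lomitapide dose, so an event in an enrolled patient who is scanned but never dosed is left out of the sub-study safety summary

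*Protocol*

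**What the plan says.** Four parts of the protocol bear on this.

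- **Who is in the safety set.** Section 8.5.3.3 defines it as "all enrolled patients who have received at least one dose of lomitapide". There is no other condition, and the definition is not deferred to the SAP.
- **What the set is used for.** Section 8.5.4.5 gives it two uses. The first is adverse events and serious adverse events "associated with the MRI procedures and clinical laboratory monitoring, using the safety population". The second is the registry data: "Adverse events for the sub-study safety population, collected as part of the LOWER study, will be summarized".
- **When the first procedures happen.** Section 8.3.1.1 puts the blood draw and the baseline MRI at the enrolment visit, and allows the scan "prior to initiating lomitapide therapy or within three months after initiating lomitapide therapy". Section 8.3.1.2 states a preference: "The baseline MRI should ideally be scheduled as soon as possible after enrolment and prior to initiation of lomitapide therapy".
- **Who can be enrolled.** Section 8.2.1 targets patients for whom lomitapide has been prescribed. Section 8.2.1.1 admits those just starting it as well as those who started within the previous three months. Neither section requires that a dose has been taken before the first sub-study procedure.

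**The concern.** A safety population should contain everyone exposed to the risk being described. For treatment-emergent events that means everyone who took the drug. For events caused by a scan or a blood draw it means everyone who had one. The protocol uses one drug-based set for both.

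The two sets differ for one kind of patient: enrolled, scanned and bled before the first dose, and then never dosed. Such a patient is missing from both the numerator and the denominator of the procedure-event summary. The preferred timing of the baseline scan is what makes this case possible. What is at stake is the completeness of a descriptive table, in a sub-study whose own safety question concerns the procedures.

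**Working it through.** The point rests on comparing definitions. The arithmetic only bounds its size.

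**Step 1. Follow one patient through the protocol.** Take a patient who has been prescribed lomitapide, consents, has the blood draw and baseline scan before the first dose, has a procedure-related event, and never takes a dose.

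| Place in the protocol | Condition | Is this patient covered? |
|---|---|---|
| 8.2.1, 8.2.1.1 (eligibility) | Prescribed and starting | Yes, can be enrolled |
| 8.3.1.1, 8.3.1.2 (baseline visit) | Scan before dosing allowed and preferred | Yes |
| 10.1 (reporting) | Event related to MRI or laboratory assessment, no dosing condition | Yes, reported within 24 hours |
| 10.7 (causality) | Covers relation to study procedures, and the patient who has not received lomitapide | Yes |
| 8.5.3.1 (MITT) | Readable baseline MRI, no dosing condition | Yes, if the scan is readable |
| 8.5.3.3 with 8.5.4.5 (safety summary) | At least one dose | **No** |

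The event is collected and assessed, and the patient may count in the primary efficacy population. The safety summary is the only place that leaves the patient out. Section 8.5.3 has no other population that is assigned to procedure safety.

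**Step 2. The planned number.** Section 8.4 plans 40 evaluable and at least 57 enrolled patients. With a standard deviation of 22% and a change of 10%, a two-sided one-sample t-test at 0.05 has power 0.8005 at n = 40. Enrolment is 40 / (1 − 0.15 − 0.15) = 40 / 0.70 = 57.1. Both figures reproduce. They are not in dispute; 57 is used below only as the base.

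**Step 3. How many patients could be left out.** The protocol gives no rate of never starting, so the rate r is an assumption shown as a range. The first result is 57 × r. The second is the chance of at least one such patient, 1 − (1 − r)^57, which treats patients as independent.

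| Assumed r | Expected number of 57 | Chance of at least one |
|---|---|---|
| 1% | 0.57 | 44% |
| 2% | 1.14 | 68% |
| 5% | 2.85 | 95% |

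These figures treat all 57 as scanned before dosing. Patients who started within three months before enrolment have already been dosed and cannot fall in this group. If only a share s were scanned before dosing, the expected number becomes 57 × s × r; with s = 0.5 as an example, it is about 0.3 to 1.4.

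**Step 4. Patients are not events.** An omission also needs a procedure event in one of these patients. If 1% to 5% of them had one (again an assumption), the expected number of omitted events runs from 57 × 0.01 × 0.01 = 0.006 to 57 × 0.05 × 0.05 = 0.14. For a serious event it would be lower.

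**The case against.** The strongest reply is that the group is nearly empty and nothing is lost from oversight. Section 8.1 describes the invited patients as already being treated. Those in the second inclusion category have taken the drug by definition. Section 10.1 sends every procedure event to the coordinating centre whatever the dosing status, and section 10.7 has the investigator judge its relation to the scan. Procedure safety is descriptive, so no hypothesis test depends on the set. The dose condition also suits the LOWER adverse event tables. All of this stands, and it limits the point to a minor one. It does not remove the mismatch: sections 8.2.1 and 8.3.1.2 leave room for the undosed patient, and the summary in 8.5.4.5 is tied by a stated rule to a set that excludes that patient.

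A reader might infer more in two ways, and the documents support neither.

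- **That the omission is informative, because a bad event at the baseline scan may be why a patient does not go on.** This confuses leaving the sub-study with never starting the drug. Lomitapide is prescribed in usual care, and withdrawal from the sub-study (8.3.1.5) is separate from stopping lomitapide (8.3.1.6). A patient who leaves after a bad scan but takes one dose stays in the safety population, which has no follow-up condition. Nothing in the protocol links a procedure event to not starting treatment.
- **That a reported count of serious events could fall from one to none.** That is possible but is a worst case. Step 4 shows that even under the higher assumed rates the expected number of omitted events of any kind is well below one.

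**Conclusion.** The point holds as a minor mismatch between an analysis population and the events analysed in it. For MRI and blood-draw events, sections 8.5.3.3 and 8.5.4.5 together leave out any enrolled patient who had a procedure but no dose, although the protocol prefers the first scan to come before dosing. The event would still be reported; it would be missing only from the summary.

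The size is probably small: about 0.6 to 3 patients on the planned 57. This rests on an assumed never-start rate of 1% to 5% and on all patients being scanned before dosing, so the number falls if some are scanned afterwards. The primary efficacy analysis, alpha and power do not use this population and do not change.

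**What to change.** Add to section 8.5.3 a procedure-safety set of all enrolled patients who underwent any sub-study MRI or blood draw. In section 8.5.4.5, name this set for adverse events and serious adverse events related to those procedures. Keep the present population, with its dose condition, for the treatment-emergent and drug-related adverse event tables taken from LOWER and for the exposure summary.

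The cost is one sentence and one population flag. The flag needs only a record that a sub-study scan or blood draw took place, which the sub-study generates itself. Data collection, reporting rules, sample size and patient management stay as they are.

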8.5.4 Statistical Analysis

8.5.4.1 Baseline Evaluations and Disposition

Demographic and baseline disease characteristic data will be collected as part of LOWER and summarized for patients enrolled in this study. Data to be tabulated will include demographic information such as sex, age, and race, as well as information on variables which may be potential confounders including medications, procedures, comorbidities (including hypertension) and conditions (including smoking status, alcohol use, and

diabetes) that can affect atheroma progression. The number of study subjects included in each analysis population will be summarized, including the number who withdraw from the study or discontinue lomitapide and the reasons for withdrawal or discontinuation.

8.5.4.2 Primary Efficacy Endpoint Analysis

The primary efficacy endpoint is the percent reduction from baseline in carotid vessel wall area at the two-year evaluation. The primary analysis will be a one-sample t-test on the within-subject percent reduction in average carotid vessel wall area using the MITT population. Given that these patients have substantial cardiovascular disease, it is unlikely that reduction in atheroma burden would occur over time in the absence of lipid-lowering therapy. Further, it is logical to believe that any reduction in carotid vessel wall area would be of benefit to the patient, and that this reduction would accompany the anticipated reduction in LDL-C from lomitapide therapy. Based on the sample size calculation, the null hypothesis to be tested is that the percent reduction in carotid vessel wall area is 0%, versus the alternative that the reduction is 10% or more; however, it is also important to consider the minimal detectable difference that may be achieved. The minimal detectable difference would range from 3% to 4.2%, with achieved sample sizes in the range between 40 and 57 subjects. The minimal detectable difference represents the lower bound of the two-sided, 95% confidence interval calculated when data are available for analysis and presumes the targeted 10% point estimate for reduction in carotid vessel wall area has been achieved, and the standard deviation is consistent with the estimated 22% used as the basis for the sample size calculations. It is believed that the absence of progression as determined by excluding a change in atheroma size of >3% would be clinically important.

Descriptive statistics will also be presented, including the sample number, mean, median, standard deviation, minimum and maximum values, as well as a two-sided, 95% confidence interval. Absolute data values, including arithmetic change from baseline, will be presented descriptively, in addition to percent change from baseline.

This analysis will be conducted when two-year carotid vessel wall area measurements have been obtained from all study subjects, including potentially imputed values from MITT subjects missing the two-year measurement. Missing observations at the two-year time point will be estimated using a multiple imputation (MI) procedure, as outlined in [Section 8.5.6](#). The missing data will be estimated as the absolute value of the MRI

measurement, and this imputed value will be used for calculation of percent change from baseline.

Exploratory analyses of the potential impact of covariates such as age, sex and baseline atheroma burden on the primary endpoint will also be performed. These analyses will help determine if the percent reduction from baseline in carotid vessel wall area at the two-year evaluation is influenced by these covariates. In addition, the potential influence of confounding factors will be evaluated through descriptive, univariate analyses. Multivariate analyses to evaluate the potential for interactions among the various confounding variables will not be performed, since the sample size limitations may not allow this to be done with precision. These confounding variables are factors that could influence change in atheroma burden over time, and will include:

- Changes in existing therapies or procedures or the administration of new therapies or procedures that may influence the progression of atheroma
- Co-morbidities including cardiovascular disease, hypertension, diabetes mellitus, and obesity
- Smoking status and alcohol use

Changes in factors while on study will be included in these analyses as long as there is at least 6 months between the change and the MRI data obtained at 2 years.

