8.4 Study Size

Based on published information from a randomized, placebo-controlled study on change in carotid vessel parameters as assessed by MRI (Fayad, et.al, 2011), the standard deviation of percent change from baseline to 24 months in carotid vessel wall area was estimated to be 22%. Detection of a 10% change from baseline to 24 months in carotid vessel wall area, at a two-sided α -level of 0.05 with 80% power, requires 40 evaluable patients. In order to obtain 40 evaluable patients at the two-year primary endpoint, at least 57 patients with a baseline readable MRI will be enrolled. The 57 patients to be enrolled accounts for a dropout rate of 15% over the two-year period and a 15% unreadable/unusable MRI rate.

After 20 evaluable patients have two-year MRI evaluations, a sample size re-estimation will be performed only if the conditional power of the Z-test statistic falls within the promising zone as defined by Mehta and Pocock (Mehta et. al., 2011). Further information regarding this analysis (including maximum allowable sample size) is described in Section 8.5.5. If the conditional power does not fall within the promising zone, no sample size re-estimation will be performed and the study will continue as planned (Mehta, et.al, 2011).

Should patient enrolment be much lower than anticipated, Aegerion Pharmaceuticals will propose additional measures to increase patient enrolment including opening the sub-study to other countries or regions if necessary.

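### The 3% to 4.2% given as the minimal detectable difference is a lower confidence limit that presumes a 10% result; the detectable difference is 7.0% to 5.8% (significance threshold) or 10.0% to 8.3% (80% power)

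*Protocol*

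**What the plan says.** Section 8.4 takes a 10% change over 24 months as the effect to be shown, and says that this, "at a two-sided α -level of 0.05 with 80% power, requires 40 evaluable patients". The SD of percent change is taken as 22%.

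Section 8.5.4.2 fixes the test: "The primary analysis will be a one-sample t-test on the within-subject percent reduction in average carotid vessel wall area using the MITT population". The null is a 0% reduction, "versus the alternative that the reduction is 10% or more". The section then adds: "The minimal detectable difference would range from 3% to 4.2%, with achieved sample sizes in the range between 40 and 57 subjects". It explains that this figure is the lower bound of the two-sided 95% confidence interval, on the presumption that the point estimate is 10% and the SD 22%. It closes on lack of progression, and holds that "excluding a change in atheroma size of >3% would be clinically important".

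**The concern.** A minimal detectable difference is normally either the smallest observed effect that reaches significance or the smallest true effect that the study detects with stated power. The figure in section 8.5.4.2 is neither. Three signs show this without any calculation:

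- It rises from 3% to 4.2% as the sample grows from 40 to 57. A detectable difference falls as n rises.
- It sits beside a sample size that gives 80% power for 10% at n = 40. The same 40 patients cannot have a minimal detectable difference of 3% on that basis.
- It depends on having observed 10%, so it describes one favourable result and not the sensitivity of the test.

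The stake is interpretation. A reader who takes the term at face value would think that a mean reduction of 3% to 4% could be shown. The next use of 3%, as a margin for absence of progression, adds to the confusion: there 3% refers to a change to be excluded, whereas in the sentence before it was a lower limit for a reduction.

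**Working it through.** **Inputs.** Two-sided alpha 0.05, 80% power, effect 10% and SD 22% (section 8.4); one-sample t-test against 0%, and n = 40 and n = 57 (section 8.5.4.2). Below, n is the number of patients contributing an observed value.

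**1. The planned sample size.** Noncentral-t power for a true 10% reduction is 80.05% at n = 40 and 79.0% at n = 39, so 40 is reproduced. So is the enrolment target: 40/(1 − 0.30) = 57.1.

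**2. The stated 3% and 4.2%.** Half-width = t(0.975, n − 1) × 22/√n.

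- n = 40: 2.023 × 3.479 = 7.04; 10 − 7.04 = 2.96
- n = 57: 2.003 × 2.914 = 5.84; 10 − 5.84 = 4.16

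Both match, which confirms that the figures are lower confidence limits given a 10% estimate.

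**3. What the study can detect.** The half-width is itself the smallest observed reduction with p < 0.05. The 80%-power value is solved from the noncentral t distribution.

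| | n = 40 | n = 57 |
|---|---|---|
| Stated in the protocol | 3% | 4.2% |
| Smallest significant observed reduction | 7.0% | 5.8% |
| Smallest true reduction with 80% power | 10.0% | 8.3% |
| p-value if 3% is observed | 0.39 | 0.31 |
| p-value if 4.2% is observed | 0.23 | 0.16 |
| Power if the true reduction is 3% | 13% | 17% |
| Power if the true reduction is 4.2% | 22% | 29% |

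**4. Size of the overstatement.**

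- Against the significance threshold: 7.04/2.96 = 2.4 at n = 40; 5.84/4.16 = 1.4 at n = 57
- Against 80% power: 9.99/2.96 = 3.4 at n = 40; 8.31/4.16 = 2.0 at n = 57

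**5. Absence of progression.** Section 8.5.4.2 attaches no confidence limit or direction to the 3% margin. Assume that the upper limit of the two-sided 95% interval for percent change must lie below +3%. The probability of meeting this is P(T > t(0.975, n − 1)), where T is noncentral t with noncentrality (true reduction + 3)/(22/√n).

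| True reduction | n = 40 | n = 57 |
|---|---|---|
| 0% | 13% | 17% |
| 5% | 61% | 77% |
| 10% | 95% | 99% |

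**The case against.** The strongest reply is that the protocol hides nothing. The explanation that follows the figure says that it is a confidence bound and names the presumed 10% estimate and the 22% SD. The subtraction is right for the quantity so defined. The design sensitivity is stated correctly in section 8.4, where 10% at 80% power for 40 patients agrees with the recomputed 9.99%. Nothing operative uses the 3% to 4.2%: the sample size, the t-test, the multiplicity gate and the sample size re-estimation rule stand as they are.

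All of this stands, and it limits the point to a label and its interpretation. It does not remove it. Explaining how a number was built does not make it a detectable difference, and the section offers it as a measure of what the study may achieve.

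A reader might go further and infer that stabilisation is unlikely to be shown. The protocol's assumptions do not support that. The low probabilities of 13% and 17% hold only if the true change is zero; under the planned 10% reduction they are 95% and 99%. The two-sided 95% interval that section 8.5.4.2 already plans is enough to judge the +3% margin, so no further test is needed.

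A reader might also take the alternative of 10% or more to change the test. The sentence presents it as based on the sample size calculation, the null is 0% and alpha is two-sided. It is loose wording, since true reductions between 0% and 10% fall under neither hypothesis, but no decision depends on it.

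**Conclusion.** The point holds as a misstatement of sensitivity. What section 8.5.4.2 calls the minimal detectable difference is the lower 95% limit after an observed 10% reduction. The detectable difference is 7.0% (n = 40) to 5.8% (n = 57) by the significance threshold, or 10.0% to 8.3% at 80% power. The overstatement runs from 1.4-fold to 3.4-fold, depending on the definition and on n, so no single multiple describes it.

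It is not a calculation error, and the documents do not support a claim that the study is wrongly sized or wrongly tested.

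The figures rest on the protocol's SD of 22%, a t-test and n observed values. If some of the 57 values are imputed, the n = 57 column is a best case. The probabilities for excluding progression also rest on reading the 3% margin as an upper 95% limit below +3%, which the protocol does not spell out.

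**What to change.** In section 8.5.4.2:

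1. Describe 3.0% (n = 40) to 4.2% (n = 57) as the expected lower 95% confidence limit if a 10% reduction is observed with SD 22%, and drop the term minimal detectable difference for it.
2. If a minimal detectable difference is wanted, give 7.0% (n = 40) to 5.8% (n = 57) as the smallest significant observed reduction, or 10.0% to 8.3% for 80% power, and say which definition is used.
3. If absence of progression is to be concluded, define it as the upper 95% limit of percent change below +3%. State its probability for n = 40 and n = 57 across scenarios: 13% and 17% for no true change, 61% and 77% for a true 5% reduction, 95% and 99% for a true 10% reduction. Giving only the first or only the last pair would mislead.
4. As a minor point, state the hypotheses as mean percent change equal to 0 versus not equal to 0, with 10% as the planning value.

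The cost is wording, carried into the SAP where it repeats these statements. The stated sensitivity becomes less favourable. Sample size, test and decision rules do not change.

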8.5.6 Missing Observations

It is unlikely that patients would withdraw from the trial due to the nature of this disease; however, this possibility must be addressed. Patients will be strongly encouraged to continue in the study, and if withdrawal is necessary, they will be encouraged to obtain an MRI prior to discontinuation. Missing data for the primary endpoint of carotid vessel wall area (CVWA) obtained at 2 years, due to an unavailable or unreadable MRI at year 2, is also possible. To help minimize unreadable MRI results, patients with follow up MRIs that are considered unreadable will be requested to have a repeat MRI performed within the 2 month window. A thorough evaluation will be performed prior to data analysis, to determine the causes for any unavailable MRI results at 2 years. In particular, the possibility that missing MRI results are related to response to lomitapide therapy will be evaluated, in order to determine if MRI data are missing at random or not. For patients with no available readable MRI at 2 years, the following imputation method will be used.

For patients that could reasonably be considered to have data missing at random, such as resulting from inability to travel to the MRI center, a standard multiple imputation technique, using the predictive characteristics of complete cases (patients with 2-year

MRI data), will be used to account for these missing data in analysis. These predictive characteristics will include, for example, age, sex, lipid measurements over time, MRI results obtained prior to 2 years, etc. For patients whose data cannot reasonably be determined to be missing at random, an approach to multiple imputation will be used wherein the value to be used in each iteration of the method will be a random selection of a data point from the set of values from all patients with an available percent reduction from baseline in carotid vessel wall area at the two-year evaluation who have shown an increase in CVWA (worsened). This approach would therefore apply a conservative value that also would not artificially decrease variability.

Similar methods will be used for the assessment of, and imputation for, secondary endpoints as appropriate. Sensitivity analyses of the primary endpoint will be performed to assess the effect of missing data on the two-year endpoint, including repeated measure mixed model procedures and complete-case analysis.

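### Sections 8.5.4.2 and 8.5.6 do not fit on the scale of imputation: a worsened donor's absolute wall area need not score the recipient as worsened

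*Protocol*

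**What the plan says.** Section 8.5.4.2 makes the primary analysis a one-sample t-test on within-patient percent reduction in average carotid wall area in the MITT population. Missing two-year values are multiply imputed as outlined in 8.5.6. The same paragraph fixes the scale without separating types of missingness. Its wording is "The missing data will be estimated as the absolute value of the MRI", where the object is the wall-area reading itself. The sentence then adds that "this imputed value will be used for calculation of percent change from baseline".

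Section 8.5.6 has two routes. Data judged missing at random go to standard multiple imputation, with predictors such as age, sex, lipids and earlier MRI results. The other route opens with: "For patients whose data cannot reasonably be determined to be missing at random, an approach to multiple imputation will be used". In each iteration the value is "a random selection of a data point from the set of values from all patients with an available percent reduction from baseline" in carotid wall area at two years, restricted to patients whose wall area rose. The stated justification is: "This approach would therefore apply a conservative value that also would not artificially decrease variability".

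Section 8.5.6 does not say whether the drawn value is the donor's percent change or the donor's two-year area. It has no step that links the draw to the recipient's baseline.

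**The concern.** Donors qualify by change within themselves. An absolute wall area, however, also reflects how large the donor's vessel is. Once that area is divided by another patient's baseline, the sign of the result depends on the relative size of the two vessels as well as on the donor's worsening. The absolute scale in 8.5.4.2 therefore removes the patient-level guarantee on which 8.5.6 rests its claim to be conservative.

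The missing-at-random route does not have this problem, because its predictors include the patient's own earlier MRI results.

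At stake is the primary test. Two analysts following the protocol could draw on different scales and report different primary p-values. Section 8.5.6 also extends similar methods to the secondary endpoints.

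**Working it through.** **The plan's own figures.** With a 10% change, SD 22% and two-sided alpha 0.05, a one-sample t-test with n = 40 has power 0.8005. Enrolment is 40/(1 - 0.30) = 57.1. The minimal detectable difference is 10 - t(0.975, n-1) x 22/sqrt(n), which is 2.96 at n = 40 and 4.16 at n = 57. The stated 40, 57 and 3% to 4.2% all reproduce, so -10% and 22% are used below.

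**One pair of patients (illustrative areas, not from the protocol).** A donor goes from 40 to 46 mm2: 46/40 - 1 = +15%, worsened. The recipient's baseline is 55 mm2.
- Absolute draw: 46/55 - 1 = -16%, scored as regression.
- Percent draw: 55 x 1.15 = 63.25 mm2, scored as +15%.

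**Donor pool on the percent scale.** For change ~ N(-10, 22):
- P(change > 0) = 1 - Phi(10/22) = 0.325.
- With lambda = phi(0.4545)/0.3247 = 1.108, the donor mean is -10 + 22 x 1.108 = +14.4%.
- The donor SD is 22 x sqrt(1 + 0.4545 x 1.108 - 1.108^2) = 11.6.
- No imputed value is a reduction.

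**Absolute scale.** Imputed change = 100 x [WA0(donor) x (1 + d/100)/WA0(recipient) - 1], where d is the donor's percent change. The simulation used 2 million patients per scenario, lognormal baselines, and a recipient unrelated to the donor. The baseline CV and the correlation r between baseline and percent change are assumptions; the protocol gives neither.

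| Baseline CV | Reductions, r = 0 | Mean / SD, r = 0 | Reductions, r = -0.3 | Mean / SD, r = -0.3 |
|---|---|---|---|---|
| 10% | 23% | +15.5 / 20 | 28% | +11.6 / 18 |
| 15% | 29% | +17.0 / 28 | 36% | +10.9 / 25 |
| 20% | 33% | +19.0 / 36 | 41% | +10.9 / 32 |
| 25% | 36% | +21.5 / 46 | 45% | +11.3 / 40 |
| 35% | 40% | +28.4 / 67 | 49% | +13.7 / 57 |

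At r = 0, the share beyond -10% is 8/16/21/26/32% down the table. Widening to CV 5-50% and a true mean change of 0 or -10% gives reductions in about 10% to 52% of draws.

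**Effect on the overall mean.** Assume 4 of 57 patients fall under the rule and the other 53 average -10%.
- Percent scale: (53 x -10 + 4 x 14.4)/57 = -8.3%.
- Absolute scale, CV 25%, r = 0: (-530 + 4 x 21.5)/57 = -7.8%.
- Absolute scale, CV 25%, r = -0.3: (-530 + 4 x 11.3)/57 = -8.5%.

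**Effect on the test.** I simulated the 57-patient t-test, pooled by Rubin's rules, with the same 4 patients imputed.
- True mean -10%, r = 0: power is about 79% on the percent scale, against 72/57/42% on the absolute scale at CV 15/25/35%. The 79% refers to 57 patients with four unfavourable imputations; its closeness to the planned 80% is a coincidence.
- True mean -10%, r = -0.3, CV 25%: about 72% on the absolute scale.
- True mean 0, with 4 or 8 patients imputed: false claims of reduction are at most 1.0% on either scale, against a nominal 2.5% in that direction.

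**The case against.** The strongest reply is that the two sections can be read together. The only value that 8.5.6 names when it describes the donor set is a percent reduction. Drawing that percent and multiplying by the recipient's baseline gives an absolute area, which is what 8.5.4.2 asks for, and 8.5.4.2 itself defers to 8.5.6. This reading is available and sensible, and the fix below adopts it. But the protocol does not state the multiplication, and the one sentence that names a scale says absolute.

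A reader might infer that the rule would manufacture a benefit for lomitapide. The documents and the figures do not support that. The mean imputed value shows worsening in every scenario, and false claims of reduction stay below nominal. With r = 0 the overall mean moves away from benefit. With r = -0.3 it moves toward benefit by at most about half a point, even with 8 of 57 imputed.

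A reader might also infer that about a third of withdrawn patients would be scored as regression. That share matches a baseline CV near 20% with r = 0, and the protocol gives no CV. Nor is the rule about withdrawal as such: it covers patients whose missingness cannot be called random. The plan allows for 57 - 40 = 17 non-evaluable patients, and an unknown part of them would fall here.

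Two further replies have weight. Section 8.5.6 plans complete-case and mixed-model sensitivity analyses, which do not use donor values and would help to expose a distortion. The SAP, which is not shown, may state the unit. Neither removes the mismatch between two protocol sections that govern the primary analysis.

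**Conclusion.** The point holds as a mismatch that should be fixed; it is not a fatal flaw. Followed literally, 8.5.4.2 undercuts the stated purpose of the donor rule in 8.5.6. About 23-40% of the not-at-random imputations would be reductions at baseline CV 10-35% with r = 0, or 28-49% with r = -0.3. Their SD would be about 20-67 or 18-57 points, against 11.6 on the percent scale.

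The cost falls on patient-level conservatism, precision and power, and so mainly on the sponsor's chance of a positive result. Type I error is not raised. That the protocol's wording leaves the scale unreconciled is certain. The sizes rest on the protocol's -10% and 22% and on assumed values for the CV, the correlation and the number of patients under the rule.

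**What to change.** In 8.5.6, state that for patients not judged missing at random the donor's percent change is drawn in each iteration and applied to the patient's own baseline: WA(24) = WA(0) x (1 + donor percent change/100). Add a cross-reference in 8.5.4.2 noting that this supplies the absolute value required there. Leave the missing-at-random imputation as it is, and carry the same wording into the SAP and to the secondary endpoints that use the rule.

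The cost is one sentence and one cross-reference, with no new data and no change in sample size. It should be settled before two-year results are seen.
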